5.2 Exploratory Objectives and Endpoints

To assess pharmacodynamics (PD) properties of HM15211 after single SC doses in comparison to placebo on:

- Lipid metabolism:
 - Total cholesterol
 - o Low-density lipoprotein (LDL)
 - High-density lipoprotein (HDL)
 - Very low-density lipoprotein (VLDL)
 - Triglycerides
 - o Free fatty acid (FFA)
- Body weight
- Glucose metabolism:
 - o Fasting plasma glucose (FPG)
 - o Insulin
 - o C-peptide
- Incretin secretion:
 - o Glucagon (GCG)
 - o Leptin
 - Glucagon-like peptide-1 (GLP-1)
 - o Gastric inhibitory peptide (GIP)
- Inflammatory marker:
 - o C-reactive protein (CRP)

6.0 STUDY DESIGN AND DESCRIPTION

6.1 Study Design

This is a first-in-human, randomized, double-blind, SAD study to evaluate the safety, tolerability, and PK of HM15211 as primary objectives in healthy obese subjects.

The study will be conducted in five sequential cohorts (cohort 1 to 5) comprising a total of up to approximately 40 subjects. Each cohort will enroll subjects to ensure that at least 8 subjects per cohort will complete the study. Drop-outs may be replaced in order to have 8 completed subjects in each cohort. Subjects will be allocated into sequential dosing cohorts based on their order of entry into the study and be randomized to investigational product (IP) or placebo in a 3:1 ratio, with 6 subjects on IP and 2 subjects on placebo. Cohorts may partially overlap after at least 6 subjects have completed at least D10 and a dose escalation decision has been made.

Dosing will follow a sentinel approach with the dosing between the first 2 subjects (1 on active, 1 on placebo) and the remainder of the cohort at least 24 hours apart. A minimum of 10-days between the start date of consecutive dose levels will be maintained. Based on available safety, tolerability, and PK data of each cohort, and following a safety review and dose escalation meeting between the investigator and the sponsor, dose escalation to the next cohort may proceed. If dose escalation is stopped (please see dose escalation stopping criteria in section 6.4.1), dose de-escalation may occur in additional cohorts, to further refine clinically relevant dose levels.

Each subject will undergo a screening visit, followed by one in-house/ treatment period per subject. Two additional outpatient visits will occur, prior to a final follow-up visit that will conclude subject study participation.

The duration of subject participation in this study, including screening, treatment and follow-up will approximately be 9 weeks for subjects.

Figure 6-1 Study Design Schematic

[figure not shown]
[figure not shown]

Figure 6-2 Dose Escalation Schematic

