Subjects	Healthy Obese Subjects

Number of	Approximately 40 subjects, divided in 5 cohorts with 8 subjects	
Subjects	per cohort.	
Summary of Study Design	This is a double-blind, randomized, placebo controlled, SAD study to investigate the safety, tolerability, and PK of the subcutaneous (SC) administration of HM15211 in healthy obese subjects.	
	The study will be conducted in 5 sequential dosing cohorts, enrolling 8 subjects per cohort. Cohorts may partially overlap, if dose escalation decision after the Day 10 Visit has been made. Subjects will be randomized to HM15211 or placebo in a ratio of 6:2 (6 on active, 2 on placebo).	
	Dosing will follow a sentinel approach with dosing at least 24 hours apart. Based on available safety, tolerability, and PK data, and following a safety review and dose escalation meeting between the investigator and the sponsor, dose escalation to the next cohort may proceed. If dose escalation is stopped, dose deescalation may occur in additional cohorts, to further refine clinically relevant dose levels.	
	Adjustments to the procedures may occur after the review of available safety and PK data:	
	 Adjustments to the number of study cohorts may occur: Additional cohorts may be enrolled and proceed at a higher or a lower dose. If deemed appropriate by the investigator and sponsor, there may be more than one cohort investigated at the same dose level. 	
	• Adjustments to the 24-hr BP and HR monitoring: After the evaluation of the first cohort, tests may be rescheduled, or measurement periods may be focused on specific days to capture the 24-h measurement around the PK _{peak} .	
	 Adjustments to the visit schedule: If PK data suggest, additional sampling times and/or outpatient visits may be added to the study schedule. 	
	Each subject will undergo a screening visit, up to 28 days prior to the first dosing.	
	Each subject will undergo one in-house period of 9-day duration, two outpatient visits, and a follow-up visit.	
	Screening:	

A Screening Visit will be performed up to 28 days prior to the first dosing to identify eligible subjects for the study.

In-house Period:

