4.5 Dose Escalation Algorithm

The proposed dose escalation algorithm for HM15211 may include the following steps:

Table 4-2 Sample Allocation and Dose Escalation

Cohorts	Number of Subjects	Treatment Period	
Cohort 1	N=6	HM15211- 0.01 mg/kg	
	N=2	Placebo	
Cohort 2	N=6	$HM15211 \le 0.02 \text{ mg/kg}$	
	N=2	Placebo	
Cohort 3	N=6	$HM15211 \le 0.04 \text{ mg/kg}$	
	N=2	Placebo	
Cohort 4	N=6	$HM15211 \le 0.08 \text{ mg/kg}$	
	N=2	Placebo	
Cohort 5	N=6	$HM15211 \le 0.16 \text{ mg/kg}$	
Conort	N=2	Placebo	

Each subject will be randomized to HM15211 or placebo according to the table above. The dose will be 0.01 mg/kg, based on the body weight measured prior to dosing. For dose calculation and rounding, please refer to the Operational Manual/Pharmacy Manual.

After at least 6 subjects ($n \ge 4$ subjects on active drug HM15211) in each cohort have completed at least Day 10, safety and available PK data will be reviewed and a dose decision/ dose escalation decision for the subsequent cohort will be made by the Sponsor and the Investigator. Doses between cohorts will not exceed a 2-fold increase relative to the specified doses stated in the Table 4-3 above. Following the dose escalation decision, the procedures for the subsequent cohorts will be identical to those described above.

Adjustments to the procedures/cohorts may occur after the review of available safety and PK data:

- Adjustments to the number of study cohorts may occur: Additional cohorts may
 be enrolled and proceed at a higher or a lower dose. If deemed appropriate by the
 investigator and sponsor, there may be more than one cohort investigated at the
 same dose level.
- Adjustments to the 24-hr BP and HR monitoring: After the evaluation of the first cohort, tests may be rescheduled, or measurement periods may be focused on specific days to capture the 24-h measurement around the PK_{peak}.
- Adjustments to the visit schedule: If PK data suggest, additional sampling times and/or outpatient visits may be added to the study schedule.

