6.3 Rationale for Study Design and Endpoints

This SAD study will assess the safety and tolerability as well as PK of HM15211 as primary objectives.

Cohorts will be assessed in ascending order, but may overlap, to determine a clinically appropriate dose for the subjects and will include the comparison with placebo.

Randomization is used to avoid bias introduced through an association between study drug allocation order and subject characteristics.

A double-blind design has been chosen to avoid bias and to maintain the blind between the administration of the study drug and placebo.

Healthy obese subjects will participate in the study, as these subjects are an important target population for the novel triple agonist. Enrollment criteria will favor the target population, as body mass index will be limited to ≥ 30 to ≤ 40 kg/m².

After PK modeling, C_{max} is expected to be reached approximately 3 days after dosing. As this is a first-in-human study, measurements for the assessment of cardiovascular events will start right after dosing and will continue until Day 4. After evaluation of the PK values in the initial cohort(s), the monitoring period will be adjusted, to ensure that the 24-h period around the PK_{peak} is captured.

The proposed PK endpoints are well-established, commonly used parameters to characterize pharmacological profiles of drugs. For the PK endpoints, blood samples for determination of HM15211 will be analyzed using a validated assay.

This is an exploratory study. No formal sample size calculation and no statistical hypothesis testing will be performed.

The study will be conducted at a specialized early phase research centre, where the subjects will be under supervision of physicians, research nurses and additional medical staff experienced in conducting early phase clinical studies investigating new metabolic compounds.

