6.4 Study Discontinuation and Stopping Criteria

6.4.1 Dose Escalation Stopping Criteria

Dose escalation will be stopped if one of the following conditions apply:

• Death of a subject (AE grade 5 toxicity) in one cohort, at any time, that is considered related to the IP, judged by the Investigator

- One subject in a cohort develops an AE ≥ Grade 3 toxicity, that is considered related to the IP, judged by the Investigator
- One subject in a cohort develops an AE Grade 2 toxicity that persists for more than 7 days and is considered related to the IP, judged by the Investigator
- 2 or more of the subjects in a cohort have experienced severe adverse events, judged to be possibly or probably related to the IP, judged by the Investigator;
- 2 or more subjects receiving HM15211 develop similar clinically significant laboratory, significant ECG or vital signs abnormalities, or severe AEs in the same organ class, indicating dose-limiting intolerance. Dose escalation may proceed if after review of the data by the Investigator and discussion with Sponsor, it is concluded that the events are not drug related;
- It is determined that the limit of safety and/or tolerability has been reached. Decision will be made between Sponsor and Investigator.

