6.4.2 Criteria for Early Termination of the Study

The study will be completed as planned unless one or more of the following criteria are satisfied

- violation of Good Clinical Practice (GCP) that compromises the ability to achieve the primary study objectives or compromises subject safety.
- Failure to meet expected enrollment goals
- Administrative Reasons

In case that the Sponsor, an institutional review board (IRB)/ independent ethics committee (IEC), or regulatory authority elects to terminate or suspend the study or the participation of an investigational site, a study-specific procedure for early termination or suspension will be provided by the Sponsor; the procedure will be followed by applicable investigational sites during the course of termination or study suspension.

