10.4 Procedures

10.4.1 Collection and Recording of AEs

Collection of all AEs (serious AEs and non-serious AEs) will commence from the time the subject signs the informed consent to participate in the study until the post-treatment follow-up visit. Throughout the in-house treatment period, the Investigator will assess whether any subjective AEs have occurred. In order to avoid bias in eliciting AEs, a non-specific question, such as "How have you been feeling since your last visit?" may be asked. Subjects may report AEs occurring at any other time during the study.

All subjects experiencing AEs, whether considered associated with the use of the study medication or not, must be monitored and given appropriate medical treatment at the discretion and judgement of the Investigator until the symptoms subside and any clinically relevant changes in laboratory values have returned to baseline or until there is a satisfactory explanation for the changes observed. All AEs will be documented in the AE page of the CRF, whether or not the Investigator concludes that the event is related to the drug treatment. The event term, start and stop dates, severity, action taken with study drug and outcome, will be documented, along with the Investigator's opinion of the causal relationship between the event and the study drug.

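### The 6.4.1 criteria stop only dose escalation, so a related death or Grade 3 or higher event in a sentinel does not require a hold on the six undosed subjects of that cohort

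*Protocol*

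**What the plan says.** - **Sentinel step.** The Study Summary (2.0) says: "Dosing will follow a sentinel approach with dosing at least 24 hours apart". Section 6.1 adds who the sentinels are: the interval lies between "the first 2 subjects (1 on active, 1 on placebo) and the remainder of the cohort at least 24 hours apart". Neither place names a review of sentinel data, a person who releases the remainder, or a condition that blocks it.
- **Stopping criteria.** Section 6.4.1 opens: "Dose escalation will be stopped if one of the following conditions apply". One subject can be enough: "One subject in a cohort develops an AE ≥ Grade 3 toxicity, that is considered related to the IP, judged by the Investigator". A related death is also listed. No action other than stopping escalation is attached to any item.
- **Required safety review.** Under 4.5, once at least six subjects (at least four on active drug) have completed Day 10, "safety and available PK data will be reviewed and a dose decision/ dose escalation decision for the subsequent cohort will be made". Its subject is the next cohort.
- **After a stop.** Section 6.1 allows de-escalation in additional cohorts and does not mention undosed subjects in the current one.
- **Early termination.** Section 6.4.2 lists enrolment failure, administrative reasons and "violation of Good Clinical Practice (GCP) that compromises the ability to achieve the primary study objectives or compromises subject safety". None is triggered by an adverse event alone.

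**The concern.** A sentinel pair is useful in a first-in-human trial because a bad early outcome can spare the rest of the cohort. Here the protocol fixes in advance which events are grave enough to forbid a higher dose. It does not say that the same events suspend further injections of the dose at which they occurred. A site following the text exactly could see a related Grade 3 event in the active sentinel, stop escalation as required, wait out the 24 hours and dose the other six without breaching any rule visible in the protocol.

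The required review comes after Day 10 in at least six subjects, too late for the remainder. Sections 6.1 and 8.6 also provide for replacing drop-outs so that eight complete, with each replacement receiving the same treatment as the subject replaced. No visible text suspends that after a criterion is met.

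**Working it through.** **1. Cohort arithmetic.** The plan's total is reproduced: 5 cohorts × 8 = 40 subjects (5 × 6 = 30 active, 5 × 2 = 10 placebo). After the sentinel pair, 8 − 2 = 6 remain per cohort: 6 − 1 = 5 active and 2 − 1 = 1 placebo.

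**2. Which 6.4.1 criteria one sentinel can meet within 24 h.**
- Related death: yes.
- One related event of Grade 3 or higher: yes.
- Grade 2 lasting more than 7 days: no, there has not been enough time.
- The two items needing two or more subjects: no, not by a single sentinel.
- Limit of safety or tolerability reached: yes, but this is a Sponsor and Investigator decision.

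The gap therefore concerns two fixed triggers and one discretionary one.

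**3. What each provision does for the undosed six.**

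| Section | Provision | Effect on current-cohort dosing |
|---|---|---|
| 2.0, 6.1 | At least 24 h between sentinels and remainder | A longer wait is allowed, not required |
| 4.5 | Review after Day 10 in at least 6 subjects | Decides the next cohort's dose |
| 6.4.1 | Listed events | Stops escalation only |
| 6.4.2 | Sponsor, ethics body or regulator may suspend | Permitted, not required |
| 6.4.3 | Withdrawal of individual subjects | None for others |
| 10.6.1 | Expedited report on issues that could change administration | Permitted, not required |
| 13.2 | Deviation to remove an immediate hazard | Permitted, not required |

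No row requires a hold.

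**4. Illustration of size.** The protocol gives no event rate, so three inputs are assumed:
- p: chance of a qualifying event in an active subject, 0.01 to 0.2.
- f: share of that chance falling in the sentinel's first 24 h, 0.2 to 1.
- h: chance that dosing is held voluntarily, 0 to 0.9.

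On f, section 6.3 says: "After PK modeling, C_{max} is expected to be reached approximately 3 days after dosing". The 24 h gap is 24/72 = one third of that time, so f below 1 is likely. Subjects are taken as independent with a common p.

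Expected further events that a mandatory hold could avoid, per cohort = (f × p) × (5 × p) × (1 − h) = 5 f p² (1 − h):

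| p | f = 1, h = 0 | f = 0.2, h = 0 | f = 0.2, h = 0.9 |
|---|---|---|---|
| 0.01 | 0.0005 | 0.0001 | 0.00001 |
| 0.05 | 0.0125 | 0.0025 | 0.00025 |
| 0.1 | 0.05 | 0.01 | 0.001 |
| 0.2 | 0.2 | 0.04 | 0.004 |

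Each entry is an upper bound for its inputs, because it treats every suspension as permanent whereas dosing may resume after review.

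Given a sentinel event and no hold, the chance of at least one more among the five = 1 − (1 − p)^5: 0.049, 0.226, 0.410 and 0.672 for p = 0.01, 0.05, 0.1 and 0.2.

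**The case against.** The strongest reply is that competent investigators would hold dosing anyway and that the protocol gives them every means to do so. The 24 h is a minimum, so a longer wait is not a deviation; 6.4.2, 10.6.1 and 13.2 all leave room to suspend or change dosing; and 10.4.2 brings serious events to the Sponsor within 24 hours. This stands, and it makes a voluntary hold likely. It does not make one required, and for escalation the protocol itself chose to write fixed triggers down.

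A reader might infer that sentinels go unwatched. The protocol does not support that: "Throughout the in-house treatment period, the Investigator will assess whether any subjective AEs have occurred". Vital signs are taken at 4, 8, 12 and 24 h, injection sites are checked at 4 h, 12 h and on Day 2, ABPM and Holter run throughout, and amylase, lipase and fasting glucose are drawn on Day 2 with other pharmacodynamic samples. The first post-dose 12-lead ECG is on Day 4, but surveillance is not the gap.

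It can also be said that 6.4.1 is headed as escalation criteria and contradicts nothing, and that a hold may appear in Figure 6-2 or the Operational Manual. The first is true, but no other section supplies the missing scope. The second cannot be excluded, although the visible references to that manual concern dose calculation, ABPM and Holter.

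Finally, a written rule does not remove judgement. Relatedness is still the Investigator's call, made around the planned dosing time, and the same parties decide whether to resume. What changes is the default, and that the decision is recorded.

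**Conclusion.** The point holds in limited form and should be acted on. The stopping rule is too narrow: followed exactly, it lets five more subjects receive active drug at a dose that has just met a stopping criterion. That conclusion rests on the visible text alone and does not depend on the assumed rates.

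Two stronger readings are not supported. The protocol neither obliges the site to continue nor forbids a hold. Nor can it be said that many events would be prevented: the average gain is small across the assumed ranges, from 0.00001 to 0.2 events per cohort, all upper bounds under inputs the protocol does not supply. The 5% to 67% figures apply only if a sentinel event occurs and nobody holds dosing. The case for change is protection in that rare situation, at low cost.

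**What to change.** **Section 6.4.1**, add: *If any criterion is met, further dosing in the current cohort, including replacements, is also suspended until the Investigator and Sponsor have reviewed the data and documented the decision.* The thresholds stay as they are.

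**Sections 2.0 and 6.1**, state that the remainder is dosed at least 24 h after the sentinel pair and only after a documented, blinded Investigator review of the sentinels' available data: adverse events, vital signs, injection-site checks, ABPM and Holter data as accessible, and any Day 2 results then available (amylase, lipase, fasting glucose).

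**Cost.** A wording change and one documented review per cohort, using assessments already scheduled. The sentinels' 24 h checks (± 15 min) fall at about 08:00, the planned dosing time of the fasted remainder, so a short delay is possible on the second dosing morning. If a criterion is met, the undosed subjects wait or are rescheduled. Because the review is blinded, an event in the placebo sentinel that is judged related will occasionally cause a hold.

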6.2 Study Description

Each subject will undergo the following procedures during the study:

Screening Visit:

Before the screening takes place, potential subjects for the trial will be provided with written and oral information about the trial and the procedures involved. Subjects must sign the informed consent form (ICF) prior to entering the study. Please see section 9.1.1 for further details.

The screening visit will be performed up to 28 days prior to the first dosing day, to identify eligible subjects for the study. All assessments performed at the screening visit are stated in Table 16-1 and will be recorded in the electronic case report form (eCRF). Please see section 9.1.2 and 11.2 for further details.

In-house Period:

Subjects will check in to the clinical research unit (CRU) in the morning of Day -2 for a 9-day in-house period. They will receive standardized meals throughout their in-house stay. A 12-lead standard ECG will be performed. Subjects will be connected to an ABPM system for measurement of blood pressure (BP), and measurements will be started overnight on Day -2 to familiarize the subjects with the device. Measurements will continue until the morning of Day 4.

In the morning of Day -1, subjects will get connected to a Holter ECG for continued measurement of the heart rate activity until the morning of Day 4.

Only 24-hour monitoring data from Day -1 to Day 1 will be used for the monitoring evaluation as baseline assessments for ABPM and Holter ECG monitoring. For measuring timepoints, please see sections 9.1.14 and 9.1.15.

Subjects will be randomized to a single SC injection of HM15211 or placebo. Randomization will take place as close to the drug administration as possible.

On Day 1, after an \geq 10 h overnight fast, subjects will be dosed with HM15211or placebo at approximately 08:00 hours (t=0), through SC injection into the abdominal wall by qualified study staff. Measurements of vital signs, ECG, blood sampling for PK and PD analyses, local injection site evaluation, and laboratory parameter will be performed for safety evaluation, at timepoints stated in Table 16-1.

ABPM and Holter ECG monitoring will be continued until the morning of Day 4 for the post-dose evaluation. 24-hour monitoring evaluations will be performed together with available PK data, in order to determine the best time period for 24-h monitoring period around PK_{peak}.

Subjects will continue to stay in-house for safety evaluations, PK and PD assessments. They will be released from the CRU in the morning of Day 7 and will return for two outpatient visits on Day 10 and 17.

Outpatient Visits:

Subjects will return to the CRU on Days $10 (\pm 1)$ and $17 (\pm 1)$ for two outpatient visits. Blood samples for PK and PD analyses will be collected, and additional safety assessments will be performed as stated in the Table 16-1.

Follow-up Visit:

A Follow-up Visit will be performed on Day 30 (\pm 2) for final safety procedures. Please see Table 16-1Schedule of Events for details.

Sampling and Assessment:

Time points for study procedures and sample collection are specified in the Table 16-1.

Safety assessments will occur throughout the duration of the study, including monitoring of adverse events (AEs), clinical laboratory tests (eg, chemistry, hematology, coagulation, amylase, lipase and urinalysis), vital signs measurements (blood pressure, heart rate, respiration rate, and aural temperature), 12-lead electrocardiograms (ECGs), ABPM, Holter ECG monitoring, and physical examinations.

Local tolerability assessments will be performed by injection site inspection at specific time-points.

Immunogenicity samples for assessment of ADAbs, nAbs and anti-PEG will be taken prior to dosing, on Day 17, and at follow-up, as stated in the Table 16-1.

The PK samples will be taken in accordance with the PK sampling schedule in section 9.1.16. Sampling may be adjusted based on the results of the SDRM.

The PD samples will be taken in accordance with the PD sampling schedule in section 9.1.17. Sampling time points may be adjusted based on the results of the SDRM.

